
VIR-7831  
Vir Biotechnology, Inc.

VIR-7831-5008 (GSK Study 217114)  
Amendment 4

Potential Risk of Clinical Significance	Summary of Data/Rationale for Risk	Mitigation Strategy
	
In the COMET-ICE study in participants with mild/moderate COVID-19 at high risk of progression, IRRs that occurred within 24 hours post infusion (pyrexia, chills, dizziness, dyspnea, pruritus, rash, and other infusion-related reaction) were reported in 6 (1%) of participants in the sotrovimab arm and 6 (1%) of participants in the placebo arm. All IRRs were nonserious, and Grade 1 or 2 severity and none led to treatment pausing or discontinuation. In the sotrovimab arm, all of the cases of IRRs were considered resolved and in the placebo arm, one participant had an event considered not resolved at the time of data cut-off. In COMET-ICE, all HSRs observed in the study were nonserious, of Grade 1 (mild) or Grade 2 (moderate) severity and reported in 2% of participants who received sotrovimab and in <1% who received placebo (9 participants treated with sotrovimab; 5 participants treated with placebo). None of the reactions in either arm led to pausing or discontinuation of the infusions. All events across both treatment groups were reported as resolved or resolving at the time of data cut-off.
 
No anaphylaxis events were reported in the COMET-ICE study in participants with mild to moderate COVID-19 not requiring hospitalization at study entry.
 
No anaphylaxis or serious hypersensitivity reactions were reported in the COMET-TAIL study in participants with mild to moderate COVID-19 not requiring hospitalization at study entry.
	
 
Investigational product will be administered in the clinic with staff trained in emergency care and resuscitation procedures with emergency care kit on hand during the study intervention administration and post-therapy observation periods.
 
Investigators will be instructed to discontinue IV infusions for participants who develop Grade 3 or higher infusion reactions.
 
If a participant experiences a Grade 2 IRR, investigators will be instructed to pause the infusion. The infusion may subsequently resume at a slower pace, at the investigator's discretion, and/or after symptomatic treatment (eg, antihistamines, IV fluids).
 
Infusion-related reactions including HSRs will be categorized as AESIs (as has been done in the past for other studies).
 

VIR-7831  

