#### 5.1.2. Type of Participant and Disease Characteristics

3. Participants who have a positive SARS-CoV-2 test result within 7 days of randomization (by any validated diagnostic test e.g., RT-PCR, antigen-based testing on any specimen type)

AND

4. Oxygen saturation  $\geq 94\%$  on room air

AND

5. Have symptoms of COVID-19 defined by one or more of the following: fever, chills, cough, sore throat, malaise, headache, joint or muscle pain, change in smell or taste, vomiting, diarrhea, shortness of breath on exertion

AND

6. Participant to be dosed less than or equal to 7 days from onset of symptoms to dosing day (D1)

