#### **8.4.8. Disease-Related Events and/or Disease-Related Outcomes Not Qualifying as AEs or SAEs**

Adverse events related to expected progression, signs, or symptoms of COVID-19, unless more severe than expected for the participant's current clinical status and medical history, or resulting in hospitalization as noted in Section 8.4, should not be reported as an AE or SAE.

However, if the underlying disease (i.e., progression) is greater than that which would normally be expected for the clinical course of the disease and/or the patient's clinical status, or if the investigator considers that there was a causal relationship between treatment with study treatment(s) or protocol design/procedures and the disease progression, then this must be reported as an AE or SAE.

For example, the following constitute events NOT meeting the AE definition and that should be considered as expected progression, signs, or symptoms of COVID-19:

- hypoxemia due to COVID-19 requiring supplemental oxygen
- hypoxemia due to COVID-19 requiring non-invasive ventilation or high flow oxygen devices
- respiratory failure due to COVID-19 requiring invasive mechanical ventilation or extracorporeal membrane oxygenation (ECMO)

**NOTE:** If either of the following conditions apply, then the event must be recorded and reported as an AE or SAE (instead of a disease-related event):

- The event is, in the investigator's opinion, of greater intensity, frequency, or duration than expected for the natural history of the disease, or
- The investigator considers that there is a reasonable possibility that the event was related to treatment with study treatment(s).

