#### **8.4.9. Adverse Events of Special Interest**

Adverse events of special interest are defined as relevant known toxicities of other therapeutic mAbs or are defined from signals observed in previous studies in the nonclinical or clinical sotrovimab programs, that the sponsor will monitor throughout the study. AESIs may be updated during the study based on accumulating safety data.

Adverse events of special interest include:

- Infusion-related reactions including hypersensitivity reactions within 24 hours after infusion
- Hypersensitivity reactions occurring at any time post dose
- Immunogenicity related AEs
- Adverse events potentially related to ADE of disease. Antibody-dependent enhancement theoretically can occur via 1 of 3 previously described mechanisms described in Section 8.4.9.3.

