
The investigator is obligated to assess the relationship between study intervention and each occurrence of each AE/SAE.
 
 
A "reasonable possibility" of a relationship conveys that there are facts, evidence, and/or arguments to suggest a causal relationship, rather than a relationship cannot be ruled out.
 
The investigator will use clinical judgment to determine the relationship.
 
Alternative causes, such as underlying disease(s), concomitant therapy, and other risk factors, as well as the temporal relationship of the event to study intervention administration will be considered and investigated.
 
The investigator will also consult the Investigator's Brochure (IB) and/or Product Information, for marketed products, in his/her assessment.
 
For each AE/SAE, the investigator must document in the medical notes that he/she has reviewed the AE/SAE and has provided an assessment of causality.
 

VIR-7831  
Vir Biotechnology, Inc.

VIR-7831-5008 (GSK Study 217114)  
Amendment 4

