4.5.2. Adverse Events

Adverse events analyses including the analysis of adverse events (AEs), Serious AEs (SAEs) and other significant AEs will be based on GSK Core Data Standards. As per the protocol, AEs are collected through Week 12 and SAEs collected through Week 36.

An overview summary of AEs will be produced, including counts and percentages of participants with:

- AEs
- AEs related to study intervention
- AEs leading to permanent discontinuation of study intervention,
- AEs leading to temporary interruption of study intervention
- Grade 3 and 4 AEs
- Grade 3 and 4 AEs related to study intervention,
- Grade 3 and 4 AEs leading to permanent discontinuation of study intervention,
- Grade 3 and 4 AEs leading to temporary interruption of study intervention
- SAEs
- SAEs related to study intervention,
- Fatal SAEs
- Fatal SAEs related to study intervention.
- Local infusion/injection site reactions

Adverse events will be coded using the latest version of the standard Medical Dictionary for Regulatory Affairs (MedDRA dictionary) and graded by the investigator according to the DAIDS 2017 v2.1.

The following adverse events will be considered of special interest (AESI) and will be summarised using frequency and percentages separately.

- Systemic infusion/injection related reactions (IRR) including hypersensitivity reactions (HSR); reactions within 24 hours of start of infusion will be identified using a list of MedDRA preferred terms confirmed by the Safety team.
- Local infusion/injection site reactions (ISR) will be identified using a list of MedDRA preferred terms confirmed by the Safety team.
- Immunogenicity (Anti-Drug Antibodies (ADA)) related adverse drug reactions will be reported. These potential events of ADAs will be detected by reviewing AEs that indicate HSR in those subjects who have positive anti-drug antibodies.
- Adverse events potentially related to antibody-dependent enhancement of disease (ADE) will be reported. These potential events of ADEs will be detected by reviewing adverse event/serious adverse events for an increase in the incidence and severity of COVID complications for a participant that cannot be explained by underlying risk factors.

In addition to the AE overview summary,

- Most common AEs defined as any AE preferred term (PT) with an incidence of at least $\geq 1\%$ (approx. 2 subjects) in any of the treatment group will be summarised using frequency and percentages separately.

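### Fever or chills soon after infusion can be filed as disease-related events on investigator attribution, and no table would then show them as possible infusion reactions

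*Protocol*

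**What the plan says.** **Reporting rule.** Protocol Section 8.4.8 says that "Adverse events related to expected progression, signs, or symptoms of COVID-19, unless more severe than expected" for that participant, are not reported as AEs or SAEs. Its closing note reverses this in two cases: the investigator finds the event more intense, frequent or prolonged than the disease would explain, or sees a reasonable possibility that treatment caused it. Such an event must be reported as an AE or SAE. The examples given are hypoxemia and respiratory failure needing support, and they are only examples. Section 10.3.1 repeats the exclusion with the severity exception alone.

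**Overlapping terms.** The entry symptoms in Section 5.1.2 include "fever, chills, cough, sore throat, malaise, headache, joint or muscle pain" and, later in the list, exertional breathlessness. Section 2.3.1 reports, for the earlier placebo-controlled trial (COMET-ICE), "IRRs that occurred within 24 hours post infusion (pyrexia, chills, dizziness, dyspnea, pruritus, rash, and other infusion-related reaction"), in 6 participants (1%) on each arm, all Grade 1 or 2.

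**Endpoint.** Section 8.4.9 lists as an AESI "Infusion-related reactions including hypersensitivity reactions within 24 hours after infusion". It does not say that this definition takes precedence over Section 8.4.8. AEs, SAEs, AESIs and disease-related events (DREs) through Day 8 are all primary endpoints (Section 3).

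**Causality threshold.** Section 10.3.4 asks for facts, evidence or arguments that suggest causation, "rather than a relationship cannot be ruled out". It also requires the timing relative to dosing to be considered.

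**Derivation.** In SAP Section 4.5.2, under adverse events, "reactions within 24 hours of start of infusion will be identified using a list of MedDRA preferred terms confirmed by the Safety team". DREs go on their own form (SAP 4.3.1.1) and are summarised by overall frequency (SAP 4.5.2.1). This SAP is version 2.0, based on Amendment 3, for the IM versus IV part. Protocol Section 9.4 says that the SAP will be finalised before formal reporting of Cohort A.

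**The concern.** The substudy asks whether higher doses and shorter infusions are tolerated, and the infusion reaction is the event used in Section 9.2 as the benchmark for Cohort A (1.14%). The same symptom can be an infusion reaction or COVID-19, and the form it goes on depends on the investigator's attribution. Neither document sets a default for symptoms that begin inside the 24-hour window.

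A mild fever some hours after dosing, in a participant already unwell, is the ambiguous case. The severity exception is unlikely to apply to a Grade 1 or 2 event, and the relatedness exception needs a positive argument. If the site uses the DRE form, a derivation that searches AE terms will not find the event. With open-label treatment and no untreated arm, nothing in the data would show that events had moved from one row to the other. Attribution habits may also differ between sites.

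**Working it through.** **1. Which terms overlap.** Pyrexia and chills are in both lists. Dyspnea overlaps only in part: the entry symptom is breathlessness on exertion, and Section 5.2.1 excludes new breathlessness at rest as severe disease, so new dyspnea at rest after infusion would exceed the enrolled clinical status and go to AE reporting. Dizziness, pruritus and rash are not entry symptoms. The exposure is mainly fever and chills.

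**2. Where a Grade 1 or 2 fever within 24 hours goes.**

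| Investigator's view | Form | Counted as AESI? |
|---|---|---|
| Reasonable possibility of relatedness | AE (8.4.8 note) | Yes, under 8.4.9 |
| More severe, frequent or prolonged than expected | AE (8.4.8 note) | Yes, if the AE search matches term and onset |
| Expected symptom; relatedness not positively suggested | DRE | No |

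Only the third row leaves the AESI count.

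**3. The protocol's detection figures.** Inputs from Section 9.2: n = 200 with rate 1.14%, and n = 50 with rate 4.5%, each said to give a 90% chance of at least one event. Formula: 1 − (1 − p)^n.

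- 1 − (1 − 0.0114)^200 = 89.9%
- 1 − (1 − 0.045)^50 = 90.0%

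Both reproduce. Both take every reaction as reaching the count.

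**4. Illustration of sensitivity.** Let f be the share of true reactions filed as DREs. The documents give no value; 25% and 50% are assumed. Formula: 1 − (1 − p(1 − f))^n.

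| f (assumed) | n = 200, p = 1.14% | n = 50, p = 4.5% | Expected count, n = 200 |
|---|---|---|---|
| 0 | 89.9% | 90.0% | 200 × 0.0114 = 2.28 |
| 25% | 82% | 82% | 2.28 × 0.75 = 1.71 |
| 50% | 68% | 68% | 2.28 × 0.50 = 1.14 |

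To keep a 90% chance at n = 200, the true rate would have to be 1.145% / 0.75 = 1.53% or 1.145% / 0.50 = 2.29%, where 1.145% = 1 − 0.1^(1/200).

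**5. Comparability with the benchmark.** Sections 2.3.1 and 8.4.9.3 give 6 reactions per arm and 1057 randomised in the earlier trial. If the arms were about equal (assumed), 6 / 528.5 = 1.14%, which matches Section 9.2. An equal count on placebo suggests, as an inference only, that those reactions were counted largely by term and timing. A count that depends on attribution may not be comparable with it.

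**The case against.** A reader might infer that Section 8.4.8 removes fever, chills and dyspnea from AE reporting outright, or that most infusion reactions would be lost. The documents support neither. The note makes AE reporting mandatory when relatedness is reasonably possible, and Section 10.3.4 requires timing to be weighed. Fever and chills two hours after a monoclonal antibody infusion supply an argument for causation, since Section 2.3.1 names such reactions as a class risk. Section 10.3.1 gives infusion reactions as an example of solicited AEs. All this stands and narrows the point to ambiguous events. It does not set a default for them: solicitation concerns asking, not classifying, and Section 8.4.3 prefers open-ended questions.

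A reader might also infer that a moved event drops out of the primary endpoint, or that Cohorts B1 and B2 open on the AESI count. DREs through Day 8 are themselves primary, and the Joint Safety Review Team (JSRT) reviews relevant safety data with no AESI trigger (Section 4.1). Section 9.4.1 promises COVID-related AEs by preferred term; if that is meant to include DREs, fever would appear there, but pooled over eight days. Temperature is recorded at set times after infusion whatever the classification (Section 8.3.2), but only to 1 hour outside the lead-ins, against a 24-hour window.

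Two further limits stand. The derivation that misses DREs comes from a SAP written for the IM versus IV part, so the substudy's own analysis plan may already close the gap. And 1.14% is a reported rate: if the earlier trial used a similar rule for disease-related events, which the documents do not say, applying f to it would count the loss twice.

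**Conclusion.** The gap is real but narrow. Section 8.4.8 leaves new or worsened symptoms shared with COVID-19, mainly fever and chills, to investigator attribution within the 24 hours in which an infusion reaction is defined. An ambiguous mild or moderate event can properly be recorded as a DRE, and the only derivation supplied would not retrieve it. The event remains in a primary row but loses its identity as a possible infusion reaction.

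The size is unknown. The 82% and 68% show how sensitive the 90% figures are; they do not estimate a loss. No hypothesis test is affected, because none is planned (Section 9.1). This is a cheap improvement to the primary safety read-out and does not invalidate the design. The recording gap is in current Amendment 4 text; the derivation gap rests on the older SAP and holds only if the substudy analysis keeps the same approach.

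**What to change.** Leave the AE/DRE reporting rule as it is and add a supplementary tabulation in Protocol Section 9.4.1, the substudy SAP and the JSRT Day 8 outputs:

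- By cohort, count participants with a potential infusion reaction: any new or worsened event on the sponsor's pre-specified term list with onset within 24 hours of the start of infusion, taken from both AE and DRE records whatever the attribution.
- Show it beside the investigator-attributed infusion-reaction AESI count.
- Make sure the DRE form captures the event term and the onset date and time.
- Do not drop these events from the Section 9.4.4 analyses that exclude COVID-19 terms.
- State one origin for the window; Protocol Section 8.4.9 counts from the infusion and SAP Section 4.5.2 from its start.

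The cost is one derivation, one table, and a check or small change to the DRE form. The drawback is that the potential-reaction count will include some true COVID-19 symptoms. It should be labelled an upper bound for reactions with listed terms and read together with the attributed count.

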#### **8.4.9. Adverse Events of Special Interest**

Adverse events of special interest are defined as relevant known toxicities of other therapeutic mAbs or are defined from signals observed in previous studies in the nonclinical or clinical sotrovimab programs, that the sponsor will monitor throughout the study. AESIs may be updated during the study based on accumulating safety data.

Adverse events of special interest include:

- Infusion-related reactions including hypersensitivity reactions within 24 hours after infusion
- Hypersensitivity reactions occurring at any time post dose
- Immunogenicity related AEs
- Adverse events potentially related to ADE of disease. Antibody-dependent enhancement theoretically can occur via 1 of 3 previously described mechanisms described in Section 8.4.9.3.

##### **8.4.9.1. Systemic Reactions and Hypersensitivity Reactions**

Please refer to local or institutional guidelines for monitoring relevant adverse events encompassing infusion related reactions including hypersensitivity, angioedema, anaphylaxis,

VIR-7831  
Vir Biotechnology, Inc.

VIR-7831-5008 (GSK Study 217114)  
Amendment 4

acute anaphylactic shock and minor allergic episodes. Premedications will be permitted at the investigator's discretion and will be appropriately documented.

#### 8.4.9.2. Immunogenicity

Unwanted immunogenicity is an immune response by an organism against a therapeutic protein. This reaction leads to production of anti-drug-antibodies (ADA) which may inactivate the therapeutic effects of the treatment and, in rare cases, induce adverse events. This study will include participant follow-up for a period of 5 half-lives to assess for the development of ADA and potential impacts on safety, PK and/or efficacy.

#### 8.4.9.3. Antibody Dependent Enhancement

Antibody-dependent enhancement (ADE) of disease theoretically can occur via one of three previously described mechanisms:

1. By facilitating viral entry into host cells and enhancing viral replication in these cells
2. By increasing viral fusion with target host cells, enhancing viral replication in these cells
3. By enhancing disease pathology from viral antigen-antibody related immune complex deposition or complement activation and immune cell recruitment in target organs

The first two mechanisms are hypothesized to occur at sub-neutralizing antibody concentrations (Arvin 2020). This study will include participant follow-up for a period of 5 half-lives to assess for the potential of enhanced disease in the context of waning sotrovimab levels, which may manifest as an increased incidence of re-infection or increased severity of re-infections after recovery from initial illness. The third mechanism is hypothesized to occur at high levels of antigen (i.e., viral load) and antibody potentially leading to immune complex deposition and complement activation in tissue sites of high viral replication. This may manifest as acute deterioration temporally associated with sotrovimab dosing or as increased severity or duration of illness in sotrovimab-treated participants vs. placebo-treated participants.

As of 10 March 2021, enrollment into the COMET ICE study, evaluating sotrovimab for the treatment of non-hospitalized individuals with mild to moderate COVID-19, has been stopped based on the recommendation of IDMC. The total of 1057 participants have been randomized to either the IV infusion of sotrovimab Gen1 (500 mg dose) or placebo. Based on the Joint SRT review of blinded data, there has been no confirmed events of ADE. The ACTIV-3 TICO study of sotrovimab treatment in hospitalized participants with COVID-19 symptoms, which was terminated due to futility, did not reveal any safety concerns overall and no ADE. The COMET TAIL study did not reveal any safety concerns overall and no ADE.

As described in [Section 2.3.1](#), AEs potentially related to ADE of the disease will be reviewed by the JSRT to see if there are unusually severe manifestations of COVID-19 in treated individuals.

### 8.5. Pharmacokinetics

Blood samples for serum PK will be collected as detailed in the Schedule of Activities (Section 1.3). Instructions for the collection and handling of biological samples will be provided by the sponsor or designee in the laboratory manual.

- The actual date and time (24-hour clock time) of each sample will be recorded.

VIR-7831  
Vir Biotechnology, Inc.

VIR-7831-5008 (GSK Study 217114)  
Amendment 4

- Samples collected for analyses of sotrovimab serum concentration may also be used to evaluate safety or efficacy aspects related to concerns arising during or after the study.
- At visits during which whole blood samples are collected to obtain serum endpoints other than PK for sotrovimab, one sample of sufficient volume can be used.

Serum concentrations may be combined with data from other studies evaluating sotrovimab for the purpose of population PK model development. Pharmacokinetic analyses may be conducted to explore exposure-response relationships between PK parameters and selected antiviral variables. These analyses may include graphical plots, tabular summaries, and various linear and/or nonlinear analyses. Details of the PK analyses will be provided in the analysis plan.

## 8.6. Immunogenicity Assessments

Antibodies to sotrovimab will be evaluated in serum samples collected from all participants according to the Schedule of Activities (Section 1.3). Additionally, serum samples should also be collected at the final visit from participants who discontinued study intervention or were withdrawn from the study. These samples will be tested by the sponsor or designee.

Serum samples will be screened for antibodies binding to sotrovimab and the titer of confirmed positive samples will be reported. Other analyses may be performed to verify the stability of antibodies to sotrovimab and/or further characterize the immunogenicity of sotrovimab.

The detection and characterization of antibodies to sotrovimab will be performed using a validated assay method by or under the supervision of the sponsor or designee. All samples collected for detection of antibodies to study intervention will also be evaluated for sotrovimab serum concentration to enable interpretation of the antibody data. Antibodies may be further characterized and/or evaluated for their ability to neutralize the activity of the study intervention(s). Samples may be stored for a maximum of 15 years (or according to local regulations) following the last participant's last visit for the study at a facility selected by the sponsor/designee.

Samples will be collected in accordance with the laboratory manual and Schedule of Activities (Section 1.3).

